5.2 Exclusion Criteria

An individual who meets any of the following criteria will be excluded from participation in this study:

1. ALT or AST > 5 times the upper limit of normal.
2. Estimated glomerular filtration rate (eGFR) < 30 ml/min (including patients receiving hemodialysis or hemofiltration).
3. Pregnancy or breast feeding.
4. Anticipated discharge from the hospital or transfer to another hospital which is not a study site within 72 hours.
5. Allergy to any study medication.

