10.4 Protocol Amendment History

Version/Date	Description of Change	Brief Rationale
2.0 2MAR2020	Overall	This version addresses the comments received from the US FDA, Japanese PDMA, DSMB, IRBs, and NIAID scientific review.
	Improved clarity and brevity	Multiple areas throughout the document were reworded to improve clarity (recognized after implementation) and edited to minimize redundant statements.
1.1	Number of sites increased from 50 to approximately 75	Given the currently unpredictable epidemiology, additional sites will improve the ability to enroll the study in a timely manner.
	Sample size increased	Version 1 sample size table and statements in the text did not align. The new assumptions use a slightly smaller treatment effect (OR 1.75) and the 8-category scale and give the sample size of 440.
	Addition of phone call on Day 22	Recent information from the outbreak in China suggest some COVID-19 patients worsen between 2 and 4 weeks of illness. We added Day 22 because of concerns that the peak illness may be missed. There are also concerns if the more severe population will be discharged by Day 29.
	Ordinal scale was increased to 8 categories.	This addresses the concern raised by several reviews that “Hospitalized not on oxygen” is two separate populations – those still needing medical care and those kept in hospital just for infection control.
	Objectives and endpoints were put into table format	Multiple comments that the tabular form of objectives and endpoints (that was previously in Section 4) was much easier to read and understand.

	Added inclusion criteria for admission to hospital	This was implied throughout the document, but never stated in the inclusion criteria.
	Inclusion criteria #8	Contraceptive requirement aligned to new IB from February 21, 2020
	Phase of study	Changed to phase 3. After discussion with company, and new IB that outlines safety data of > 500 subjects, the company thought this was more accurately called a phase 3 trial.
1.2	Schedule of Assessments updated	To include Day 22. Footnotes also revised for clarity.
2.2	Background updated	To reflect current understanding of SARS-CoV, COVID-19, and new data from IB.
3.	Separating objectives about non-invasive from invasive mechanical ventilation	Elsewhere in the protocol, it was mentioned that this data would be captured separately, but it mistakenly never made into an endpoint.
	Added Day 14 mortality	To allow better assessment of short and long term mortality.

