3.3.2. Recovery and Time to Recovery

The primary efficacy outcome measure is the time to recovery. Recovery will be defined as having a value of 1, 2, or 3 on the clinical status 8-point ordinal scale. The time to recovery will be defined as the elapsed time (in days) from randomization to the earliest day at which a subject reaches recovery. Note that since clinical status assessments are recorded as defined in Section 4.3, the day that is being assessed (not necessarily the day the response is collected) will be used to determine the timing of events. For example, a subject with a score of 5 recorded on Days 1 - 3 and a score of 3 recorded on Day 4 will have a time to recovery equal to 3 days. It is also possible that a subject has a clinical status score > 3 reported for a particular day but was subsequently discharged on the same day. For these scenarios where a subject is discharged with no reported clinical score of 1, 2, or 3 will be considered recovered at the time of discharge.

Any subjects that are lost to follow-up or terminated early prior to an observed recovery will be censored at the day of their last observed assessment. Subjects who complete follow-up but do not experience recovery will be censored at the day of their Day 29 visit. All deaths within Day 29 (and prior to recovery) will be considered censored at 28 days. Note that we do not expect many subjects to worsen after discharge.

However, we will evaluate whether any discharged subjects subsequently experience a worse clinical status and sensitivity analyses will be conducted accordingly. For these analyses, subjects who recover but are later re-admitted will not be considered a recovery but will instead be censored at 28 days. Sensitivity analyses will be performed where subjects who were crossover treated with remdesivir (per April 29, 2020 Protocol Administrative Letter) will be censored at the time of remdesivir treatment initiation. In addition, the analyses will be replicated where subjects who were unblinded, regardless of whether they received crossover treatment of remdesivir or not, will be censored at the time of unblinding.

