5. SAMPLE SIZE CONSIDERATIONS

Sample Size for Primary Analysis

The log-rank test will be used to compare treatment arms with respect to time to recovery. For the log-rank test, the two key determinants of power are the total number of events (i.e., recoveries) E and the treatment-to-control ratio of the rate of recovery. The number of events required for power $1 - \beta$ to detect a recovery rate ratio of θ using a two-tailed test at $\alpha=0.05$ is approximately

$$E = \frac{4(1.96 + z_{\beta})^2}{\{\ln(\theta)\}^2},$$

where z_{β} is the $100(1 - \beta)$ th percentile of the standard normal distribution.

For 85% power, approximately 320 recoveries are required to detect a 40% increase in the rate of recovery ($\theta = 1.40$) from remdesivir. A recovery rate ratio of 1.40 is similar to, but slightly higher than the figure of 1.31 reported in Cao, Wang, Wen et al. (2020) for a lopinavir/ritonavir trial that used time to improvement by 2 categories as primary endpoint. A total of 400 recoveries is needed for a recovery ratio of 1.35 with 85% power. [Table 3](#) provides power for various recovery rate ratios.

Table 3: Number of recoveries needed for 85% power assuming a type I error rate of 5% for various recovery ratios.

Recovery ratio (θ)	Number of recoveries needed for 85% power
1.25	723
1.30	523
1.35	400
1.40	318

Sample Size for Key Secondary Analysis

The key secondary endpoint of the effect of treatment on Clinical Status at Day 15 will be analyzed using a proportional odds model. In this model, the odds ratio represents the ratio of the odds of a given score or better for the two arms of the study. The sample size to detect a given odds ratio for 1:1 randomization using a 2-tailed test at level α (Whitehead 1993) is given by

$$\frac{12(z_{\alpha/2} + z_{\beta})^2}{\theta^2(1 - \sum_{i=1}^K p_i^3)},$$

where θ is the log odds ratio, p_i is the overall probability (combined over both arms) of being in the i th category of the K ordinal outcomes, and $z_{\alpha/2}$ and z_{β} are the $1 - \alpha/2$ and $1 - \beta$ quantiles of the standard normal distribution.

[Table 4](#) displays five scenarios considered for outcome probabilities in the placebo arm for sample size determination. There is significant uncertainty with these assumptions given the limited data available.

Table 5 shows a range of sample sizes for odds ratios ranging from 1.25 to 2.5 for 85% power. For 90% power, increase the sample size by 17%.

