6.5. Missing Data

All attempts will be made to collect all data per protocol. Any data point that appears to be erroneous or inexplicable based on clinical judgment will be investigated as a possible outlier. If data points are identified as outliers, sensitivity analyses may be performed to examine the impact of including or excluding the outliers. Any substantive differences in these analyses will be reported.

For time to event outcomes, subjects who are lost to follow-up or terminate the study prior to Day 29 and prior to observing/experiencing the event will be censored at the time of their last observed assessment. Subjects who die prior to observing/experiencing the event will be censored at Day 29.

For the analysis of the key secondary outcome, subjects who are discharged but are subsequently re-admitted prior to Day 15 without a reported clinical score, their clinical score will be imputed at 7, which is the highest value for a hospitalized subject.

For the analyses of the secondary outcomes that involve clinical score (i.e. the key secondary outcome and time to improvement), if a subject is discharged from the hospital without a previously or concurrently reported clinical score of 1 or 2, then their clinical score at the time of discharge will be imputed as 2, which is the highest value for a non-hospitalized subject.

For the modified version of the ordinal score described in Section 4.3, if a subject is discharged from the hospital without a previously or concurrently reported clinical score of 2 or 3, then their clinical score at the time of discharge will be imputed as 3, which is the highest value for a non-hospitalized subject.

For the analyses of the secondary outcomes described in Section 3.3, the following imputation rules will be used for subjects who are lost to follow-up, terminate early from the study, or do not have further outcome data available after discharge for any reason:

- Days of Non-invasive ventilation/high-flow oxygen:
 - If the subject's clinical status scale is 6 at the last observed assessment, then the subject will be considered to be on non-invasive ventilation/high-flow oxygen

- through Day 29. The endpoint will be total days when assessments are available plus all imputed days following the last observed assessment.

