6.6.2. Interim Efficacy Review

Interim efficacy analyses will be conducted after at approximately 50% of total information. The information fraction at an interim analysis will be computed as $t = r/400$, where r is the number of recoveries by the time of the data freeze date for the interim analysis. The Lan-DeMets spending function analog of the O'Brien-Fleming boundary will be used to monitor the

primary endpoint using an overall two-sided type-I error rate of 0.05. Specifically, two one sided boundaries are constructed at level 0.025 using the spending function

$$\alpha^*(t) = 2[1 - \Phi\{2.241/t^{\frac{1}{2}}\}],$$

where Φ is the standard normal distribution function. Lan-DeMets software from the University of Wisconsin, now available in the R package 'lrbounds', will be used to calculate boundaries.

Conditional power will be presented as an additional guide to the DSMB. Conditional power allows computation of the probability of obtaining a statistically significant result by the end of the trial given the data accumulated thus far, incorporating and assuming a hypothesized treatment effect (e.g., the treatment effect assumed for sample size determination) thereafter. If conditional power is less than 20% under the original trial assumptions, consideration should be given to stopping the trial.

The unblinded statistical team will prepare these closed reports for DSMB review and recommendations. Analyses will be presented with blinded codes for treatment arms to protect against the possibility that the DSMB report may fall into the wrong hands. A DSMB charter will further describe procedures and membership. An additional document on statistical issues related to monitoring will be provided to the DSMB prior to interim analyses.

Section 6.2.3 describes the plan for the final analyses of the early and final analysis sets.

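### The check on unsustained recovery in SAP 3.3.2 reverses only re-admissions, so death after recovery and in-hospital relapse still count as recoveries there

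*SAP*

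**What the plan says.** The primary event is first-hit. Protocol section 3 and SAP 3.3.2 take the first day in category 1, 2 or 3 and do not require the status to last. Category 3 is reached while still in hospital.

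For subjects scored above 3 who leave the same day, SAP 3.3.2 provides that, where "a subject is discharged with no reported clinical score of 1, 2, or 3 will be considered recovered at the time of discharge". No destination is mentioned. For the secondary endpoints built on the score, SAP 6.5 provides that, for a discharge with no score of 1 or 2, "their clinical score at the time of discharge will be imputed as 2".

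On deaths, SAP 3.3.2 states: "All deaths within Day 29 (and prior to recovery) will be considered censored at 28 days". SAP 6.5 has the same limit, covering only deaths that precede the event. SAP 8.1.1 and protocol 9.4.2 state the censoring of deaths without that limit.

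On durability, SAP 3.3.2 expects few subjects to worsen after discharge, but undertakes to look for any who do and to run sensitivity analyses accordingly. The rule given is that "subjects who recover but are later re-admitted will not be considered a recovery but will instead be censored at 28 days". SAP 8.1.2 describes the analysis as concerning recoveries that did not last, and refers back to 3.3.2 for the rule. The shell, Table 18, is titled as a readmittance analysis.

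**The concern.** The stated aim is wider than the rule. Any deterioration after discharge includes death, which is the worst category of the scale, and SAP 8.1.2 speaks of unsustained recoveries in general. The rule catches one route only, a return to hospital. It misses the most serious failure, death after a counted recovery. It also cannot see a relapse in a subject who reached category 3 and was never discharged.

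This sits badly with the SAP's own reasoning in 8.1.1, where a death is thought of as a recovery time of infinity and takes the worst rank. If Table 18 agrees with the primary result, a reader will take that as evidence that the counted recoveries lasted. On the rule as written, it would show only that re-admission does not drive the result.

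**Working it through.** **1. The rules applied to four kinds of subject.**

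| Subject | Primary analysis (SAP 3.3.2) | Table 18 as written |
|---|---|---|
| Discharged, later re-admitted | Recovery | Censored at 28 days |
| Discharged, dies by Day 29, not re-admitted | Recovery (death is not before recovery) | Still a recovery |
| Reaches category 3 in hospital, returns to 4-7, not discharged | Recovery at first category 3 | Still a recovery |
| Last score 4-7, transferred to another acute-care hospital | Not stated | Not stated |

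Rows two and three are the gap in the check. Row four is a gap in the definition.

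**2. The death wording side by side.** SAP 3.3.2 and 6.5 censor only deaths before recovery. SAP 8.1.1 and protocol 9.4.2, read literally, censor all deaths by Day 29, which would turn row two into a non-recovery in the primary analysis. SAP 8.1.1 cites Section 3.3 as its source, so 3.3.2 most naturally governs. Two programmers could still build different datasets.

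**3. The transfer wording.** Entry exclusion 4 names anticipated discharge and, as an alternative, "transfer to another hospital which is not a study site within 72 hours". Transfer is thus distinct from discharge at entry, but no later rule says how one is scored. A transferred patient is still hospitalized and so does not meet category 1 or 2.

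**4. The plan's own figures.** Inputs from SAP 5 and 6.6.2: "A total of 400 recoveries is needed for a recovery ratio of 1.35 with 85% power", "using an overall two-sided type-I error rate of 0.05". Allocation is 1:1.

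E = 4(1.96 + z_β)² / (ln θ)² = 4(1.96 + 1.036)² / (ln 1.35)² = 398.8, so 399 against the stated 400. Power at 400 events is Φ(√400/2 × ln 1.35 − 1.96) = 85.1%. Total size at the protocol's 70% recovery is 400/0.70 = 571.4, so 572. All reproduce. The point concerns which events are counted, not how many are needed.

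**5. Illustration of size.** Neither document gives a rate of unsustained recovery. Assume a share x of the 400 recoveries is recoded as censored, with the ratio held at 1.35:

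| x (assumed) | Events recoded | Events left | Power at 1.35 |
|---|---|---|---|
| 1% | 4 | 396 | 84.8% |
| 2% | 8 | 392 | 84.4% |
| 5% | 20 | 380 | 83.3% |

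If the shares differ by arm, a rough approximation to the sustained-recovery ratio is θ(1 − x_R)/(1 − x_P), where R is remdesivir and P is placebo:

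- x_R = 5%, x_P = 0: 1.35 × 0.95 = 1.28
- x_R = 0, x_P = 5%: 1.35/0.95 = 1.42
- x_R = 5%, x_P = 2%: 1.35 × 0.95/0.98 = 1.31
- x_R = 2%, x_P = 5%: 1.35 × 0.98/0.95 = 1.39

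A balanced share costs little. An imbalance moves the estimate either way.

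**The case against.** The strongest reply is that the plan does not hide later deaths. SAP 8.1.2 plans a Day 29 summary by arm of recovered and alive, not recovered and alive, and died (shell Table 22, cited in the text as Table 23). SAP 9.4 analyses time to death in the ITT population, and SAP 8.2.9 reports re-admission. This stands: the deaths can be seen. What is missing is a time-to-recovery estimate with them reversed, which is what a durability check is for. SAP 8.1.2 also allows other censoring techniques, but only as an option.

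It can also be said that first-hit recovery is the protocol's explicit definition and that SAP version 3.0 postdates disclosure of the interim results (SAP 2.1), so the primary rule should not be reopened. That is a good reason to confine the changes to sensitivity analyses. Nor should a subject who slips from category 3 to 4 for a day and then goes home well be ranked with deaths. The fix allows for this.

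Stronger readings are tempting, but the documents do not support them:

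- *Hospice discharges and transfers are counted as recoveries.* Hospice appears in neither document. The discharge rule was written for same-day improvement, because each score is the worst of its day. A transfer with no further data could equally be censored as lost to follow-up under SAP 3.3.2. The classification is undefined; the SAP does not state it to be a recovery.
- *The key secondary endpoint is distorted in the same way.* The imputed 2 applies at discharge. SAP 3.3.3 uses the score collected at the Day 15 visit, the Table 34 shell defines category 8 to include death before the visit, and re-admission before Day 15 without a score is imputed as 7. The imputed 2 could matter at Day 15 only where no Day 15 status is available.
- *The protocol contradicts the SAP's expectation of little worsening.* The amendment history says that "some COVID-19 patients worsen between 2 and 4 weeks of illness". That dates from onset of illness and supports the Day 22 contact. It says nothing about worsening after discharge.

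**Conclusion.** The point holds as a defect in a planned sensitivity analysis, together with inconsistent death wording and an undefined transfer case. The unsustained-recovery check cannot detect death after recovery without re-admission, or relapse within the same hospital stay. The primary definition, the 400-event target and the 572 total are unaffected.

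The size is unknown. The figure of 4-20 events rests on an assumed 1-5% of 400. At 5%, balanced between arms, power falls from 85.1% to 83.3%. A 5% share confined to one arm would move a ratio of 1.35 to about 1.28 or 1.42. The documents give no reason to expect imbalance in either direction, so no claim of bias follows. The correction is worth making because the check as written misses the failures that matter most, and because a rule left open would be settled with results already known.

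**What to change.** 1. Leave the first-hit primary definition unchanged.
2. In SAP 3.3.2 and 8.1.2 and Table 18, recode as censored at 28 days any recovery followed by re-admission **or** by death by Day 29, in any setting. Retitle the table to match.
3. Add a version in which in-hospital return from category 3 to 4-7 means not yet recovered, with a later lasting recovery counted at its own date.
4. Reconcile SAP 3.3.2, 6.5 and 8.1.1 (and protocol 9.4.2) so that one explicit rule covers deaths after recovery. Keeping the first-hit definition implies retaining the limit to deaths before recovery in the primary analysis.
5. State, as a sensitivity analysis, that leaving the study hospital with a last score of 4-7 by transfer to another acute-care hospital is not counted as recovery.

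The cost is SAP wording, one reprogrammed table and slightly fewer events in the sensitivity analysis. Daily status in hospital, re-admission and death to Day 29 are already collected under the Schedule of Assessments. Discharge destination may need a query for the few subjects who left with a last score of 4-7.

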9. STATISTICAL CONSIDERATIONS

This study is intended to allow for two types of adaptations: 1) sample size re-estimation and 2) addition of new experimental arm(s). A brief summary is provided here. Details will be described in the statistical analysis plan (SAP).

Sample size re-estimation: The target of 400 recoveries corresponds to a total sample size that depends on the proportion of subjects who recover by Day 29. This proportion will be evaluated on pooled (i.e., blinded) data to evaluate the total sample size required. A preliminary estimate based on a 70% recovery probability is 572 patients.

Addition of new experimental therapies: If additional data become available to add an experimental therapy, the sample size will be updated accordingly. Analyses of newly added arm(s) will be performed comparing concurrently enrolled control subjects. This approach was used in the recent PALM study in patients with Ebola virus disease [Mulangu 2019]. Principles of adding arms and addressing questions of “when, what and how” to add them will be developed to guide the study team in their decision-making and will be outlined in a document on interim monitoring.

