4. INVESTIGATIONAL PLAN

4.1. Overall Study Design and Plan

This study is an adaptive, randomized, double-blind, placebo-controlled trial to evaluate the safety and efficacy of novel therapeutic agents in hospitalized adults diagnosed with COVID-19. The study is a multicenter trial that will be conducted in up to approximately 100 sites globally. The study will compare different investigational therapeutic agents to a control arm. There will be interim monitoring to allow early stopping for futility, efficacy, or safety. If one therapy proves to be efficacious, then this treatment may become the control arm for comparison(s) with new experimental treatment(s). Any such change would be accompanied by an updated sample size. Because background standards of supportive care may evolve/improve over time as more is learned about successful management of COVID-19, comparisons of safety and efficacy will be based on data from concurrently randomized subjects. An independent Data and Safety Monitoring Board (DSMB) will actively monitor interim data to make recommendations about early study closure or changes to study arms.

Recruitment will continue until there are 400 subjects with a “recovered” status (per the primary objective). The primary analysis will be based the total number of subjects enrolled to achieve 400 recoveries. An additional analysis of the moderate severity subgroup (those with baseline status of “Hospitalized, requiring supplemental oxygen” or “Hospitalized, not requiring supplemental oxygen - requiring ongoing medical care”) is also of public health importance. Hence, enrollment will be permitted until the date of April 20, 2020 to ensure 400 recoveries and provide additional data about this important subgroup. With recent enrollment rates, the total sample size may be 600 to over 800.

If any additional therapeutic arms are added, the sample size will be recalculated.

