4.2.3. Method of Assigning Subjects to Treatment Groups (Randomization)

Enrollment and randomization of subjects is done online using the enrollment module of Advantage eClinical[®].

Eligible subjects will be randomized and assigned in a 1:1 ratio to either remdesivir or placebo, with stratification by site and disease severity (Mild/Moderate disease or Severe disease). The randomization is based on a variable blocked scheme to provide an approximately balanced allocation to the treatment groups during the study. If arms are added or removed later in the study, randomization will continue in an equal allocation manner.

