6. GENERAL STATISTICAL CONSIDERATIONS

6.1. General Principles

This is a double-blind, placebo controlled randomized trial with a two-sided type I error rate of 0.05. Secondary hypotheses have been ordered according to relative importance. These will be described according to the appropriate summary statistics, e.g.

- Percentages/proportions/odds ratios for categorical data. For tabular summaries of percentages/proportions, the denominator (e.g. number of subjects with non-missing data) will be displayed.
- Means, median, and range for continuous data, median for time-to-event data.

Confidence intervals will be generated; for the primary analysis, the confidence level will take into account the group-sequential design of the trial (see Section 6.6 and Section 8.1) whereas 95% confidence intervals will be generated for secondary and exploratory outcomes. For hazard ratio and odds ratio estimates, Wald confidence intervals will be used. For other efficacy outcomes, Wilson or Score confidence intervals will be used. For safety outcomes, exact (e.g. Clopper-Pearson) confidence intervals will be used.

When calculating treatment effects (e.g. differences, hazard ratios, odds ratios) and when using treatment arm as a covariate in regression modeling, the placebo arm will be used as the reference group. For regression modeling that uses strata variables defined in Section 6.4, the first stratum listed for each variable in that section will be used as the reference group.

For the final time-to-event analyses, the following SAS pseudocode will be used to perform stratified analyses to generate stratum-specific median time to event estimates and confidence intervals, stratum-specific Kaplan-Meier curves, and to perform the log-rank test. For any unstratified analyses, code can be used after the removal of the `strata ... ;` line.

```
proc lifetest data=dataset plots=(s);
  time TimeVariable * CensorVariable(1);
  strata StrataVariable;
  test TreatmentVariable;
run;
```

Note that the interim efficacy analyses will be performed using R. For all interim and final analyses, the software used will calculate the log rank statistic using the formula in Section 8.1.1.

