6.2.3. Final Analyses

After the DSMB meeting on April 27, 2020, the interim results were provided to the sponsor and the interim analyses were performed again on an April 28, 2020 database freeze (unlocked dataset). The results of these analyses were made public on April 29, 2020. Subsequent to this, the plan for the final analyses (and corresponding datasets) was modified to the following:

- A preliminary analysis of the primary, key secondary, and major safety outcomes will be performed on unlocked, partially clean version of data and events that occurred up to April 28, 2020. This preliminary analysis dataset was used for the analyses and summaries included in the “Remdesivir for the Treatment of Covid-19 – Preliminary Report” article published in The New England Journal of Medicine on May 22, 2020 (DOI: 10.1056/NEJMoa2007764) and will be used for the preliminary report, whose summaries will coincide with the summaries provided in the article. This dataset will not be used for any further analyses apart from the preliminary report.
- A fully cleaned and locked version of data and events that occurred up to April 28, 2020 will be denoted as the “early analysis set”. Section 7, Section 8, and Section 9 denote which summaries will be provided as part of this report, but will focus largely on primary outcome, key secondary outcome, and mortality.

- The final analyses of all outcomes and planned summaries/listings will be performed on the final full locked database and provided in an addendum to the final report. This is the fully cleaned and locked version of all data and events that occurred at any time during this trial and will be denoted as the “full analysis dataset”.

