8. EFFICACY EVALUATION

8.1. Primary Efficacy Analysis

8.1.1. Primary Analyses

All the summaries described in this section will be generated for both the early and the full analysis sets.

The primary analysis uses the stratified log rank test to compare treatment to control through Day 29 with respect to time to recovery, as defined in Section 3.3. Stratification is based on mild/moderate versus severe disease at baseline. As noted in Section 3.3, all deaths within 29 days will be considered censored at Day 29 with respect to time to recovery. Conceptually, a death corresponds to an infinite time to recovery, but censoring at any time greater than or equal to Day 29 gives the same answer as censoring at Day 29; both correspond to giving deaths the worst rank.

Let MM and S denote the Mild/Moderate and Severe subgroups, respectively. The z-score associated with the stratified log rank test is

$$Z = \frac{\sum_{MM}(O_i - E_i) + \sum_S(O_i - E_i)}{\sqrt{\sum_{MM} V_i + \sum_S V_i}}$$

The sums are over recovery times t_i in the mild/moderate and severe subgroups, O_i is the number of treatment arm participants recovering at time t_i , and E_i and V_i are the null expected value and variance of the number of treatment recoveries calculated using the hypergeometric distribution. Specifically, if n_{Ti} and n_{Ci} denote the numbers of patients 'at risk' in the two arms in a given stratum at t_i , and r_i is the total number of recoveries at t_i , then $E_i = r_i n_{Ti} / (n_{Ti} + n_{Ci})$ and $V_i = r_i (n_i - r_i) n_{Ti} n_{Ci} / [n_i^2 (n_i - 1)]$, where $n_i = n_{Ti} + n_{Ci}$. The O_i , E_i , and V_i are computed separately within the mild/moderate and severe strata.

As noted in Section 6.6.2, to maintain an overall two-sided type-I error rate of 0.05, the Lan-DeMets spending function analog of the O'Brien-Fleming boundary will be used to derive the cumulative error spending and boundaries for the interim analyses.

The log rank test will be performed using the pseudocode provided in Section 6.1. The following pseudocode can be used to compute the bounds for the final analyses and compare to the calculated log-rank statistic. The `Boundaries` dataset will contain the updated boundaries calculated from the interim analyses using the actual information levels observed at the interim analyses.

```
data Parms_LogR;
  set logrankp(rename=(Statistic=Estimate));
  if Variable='TreatmentVariable';
  _Scale_='Score';
  _Stage_= AnalysisNumber;

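### In the early analysis set, deaths held at risk to 28 days outlast the April 28 data cut, so the Kaplan-Meier recovery curve runs low toward Day 29; the primary test is essentially unaffected

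*SAP*

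**What the plan says.** SAP 3.3.2 sets the rule for time to recovery: "All deaths within Day 29 (and prior to recovery) will be considered censored at 28 days". SAP 6.5 repeats it for time-to-event outcomes in general, as Day 29, which is the same 28 days from randomization. Neither section makes an exception for a data cut.

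SAP 6.2.3 defines the early analysis set as "A fully cleaned and locked version of data and events that occurred up to April 28, 2020". SAP 8.1.1 says of the primary analysis: "All the summaries described in this section will be generated for both the early and the full analysis sets". Those summaries include the median times, the hazard ratio and the Kaplan-Meier curves of Figure 2, with numbers at risk shown to Day 29.

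SAP 4.1 says "enrollment will be permitted until the date of April 20, 2020". The last subjects enrolled could thus have 8 days of follow-up at the cut, and anyone randomized after March 31 has fewer than 28.

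For subjects without recovery, SAP 3.3.2 covers loss to follow-up, early termination and completed follow-up. It does not mention subjects still on study at April 28.

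**The concern.** SAP 8.1.1 justifies the death rule by treating death as a recovery time that never comes, so that deaths rank last. That is exact when every survivor is followed to Day 29. It does not address survivors whose follow-up ends at a calendar date.

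Take two subjects randomized on April 15. One is still in hospital, unrecovered, at the cut and leaves the risk set at about 13 days. The other dies on April 20 and stays at risk for 28 days, to May 13, which is 15 days past the end of the data. Censoring now depends on outcome. Late risk sets contain every death but only those survivors who enrolled early enough, so the estimated recovery hazard is too small.

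At stake is the right-hand part of the early-set recovery curve and, slightly, the median. An arm with more deaths is pulled down more.

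**Working it through.** **Inputs from the documents.** Cut April 28; enrollment to April 20; deaths held to 28 days; 1:1 allocation (SAP 4.2.3); total N possibly 600 to over 800 (SAP 4.1), here 800. True Day 29 recovery is set at the planning value: "A preliminary estimate based on a 70% recovery probability is 572 patients" (Protocol 9). Planned control mortality at Day 15 is 2%, with 1% to 3% across scenarios (SAP Table 4).

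**Assumed.** Enrollment starts February 21. Accrual is uniform or grows exponentially at 0.05 or 0.10 per day. Mortality is 2% to 15%. Recovery and death times are exponential in shape with a 9-day half-time, truncated at 28 days.

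**The plan's own figures.** The documents give no early-set recovery estimate to reproduce. The event formula in SAP 5 does reproduce: 4(1.96 + 1.036)² / (ln 1.35)² = 398.8, against the stated 400; and 400 / 0.70 = 571.4, so 572.

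**Formula.** Let F(t) and D(t) be the cumulative incidences of recovery and death, and G(t) the share of subjects with at least t days from randomization to April 28. In large samples the daily recovery hazard is

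- SAP rule: G(t)·dF(t) / [G(t)·(1 − F − D) + Σ_{s<t} G(s)·dD(s)]
- each death censored at its own potential follow-up: G(t)·dF(t) / [G(t)·(1 − F)]

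G never increases with t, so Σ G(s)·dD(s) is at least G(t)·D. The SAP denominator can only be too large and the recovery curve only too low. This direction does not depend on the assumed inputs.

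**One step in numbers.** Take 10% mortality and growth 0.05. At t = 28, G = 0.335, F(27) = 0.693 and D(27) = 0.099. Per 800 subjects:

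- survivors at risk: 800 × 0.335 × (1 − 0.693 − 0.099), about 55.8
- recoveries: 800 × 0.335 × (0.700 − 0.693), about 1.96 before rounding
- deaths at risk under the SAP rule, 800 × Σ G(s)·dD(s): about 67.3
- deaths at risk when limited to their own follow-up: 800 × 0.335 × 0.099, about 26.5

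The hazard is 1.96 / (55.8 + 67.3) = 0.016 under the SAP rule, against 1.96 / (55.8 + 26.5) = 0.024.

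**Shortfall of the Day 29 Kaplan-Meier recovery value (percentage points; truth 70.0%)**

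| Accrual | Under 28 days at cut | 2% mortality | 5% | 10% | 15% |
|---|---|---|---|---|---|
| Uniform | 33% | 0.2 | 0.4 | 0.8 | 1.2 |
| Growth 0.05/day | 67% | 0.6 | 1.4 | 2.6 | 3.7 |
| Growth 0.10/day | 87% | 1.5 | 3.3 | 5.4 | 7.1 |

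A March 2 start changes these little (0.2 to 7.1 overall). With deaths censored at their own potential follow-up, the value is 70.0% in every cell. Across the table the Day 15 value is low by at most 0.9 points, and the median is 13.30 against 12.97 days at worst.

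**Effect on the test.** Simulation, N = 800, 2,000 trials per scenario, unstratified log-rank test; each pair is SAP rule, then corrected rule:

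- Equal mortality (10% or 15%), no treatment effect: rejection rate 0.047 to 0.054, then 0.046 to 0.054.
- Recovery ratio 1.35, equal mortality 10%, growth 0.05: hazard ratio 1.351, then 1.362; power 0.890, then 0.902.
- Recovery ratio 1.35, control mortality 15% cut by 40%, growth 0.10: hazard ratio 1.371, then 1.358; power 0.898, then 0.876.
- No recovery effect, mortality halved from 10%, growth 0.05: hazard ratio 1.016, then 1.001; rejection rate 0.046, then 0.043.

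**The case against.** The strongest reply is that little of what the SAP reports is affected. Table 14 lists medians, hazard ratios, confidence intervals and a p-value, with no Kaplan-Meier Day 29 recovery proportion. The Day 29 percentages in the Table 22 shell are crude counts, which this mechanism does not touch. Definitive analyses use the full locked database, where Day 29 follow-up is complete and the argument in 8.1.1 is exact. All of that stands, and it limits the point to the tail of Figure 2 and a small shift in the median.

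It also stands that the larger shortfalls need both steep accrual and mortality well above the planning values. A much shorter accrual period would enlarge them, but the protocol's version 2.0 amendment entry, dated March 2, 2020, already refers to a first enrollment.

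A reader might infer that the primary test is invalid. The simulations do not support this: test size holds under equal mortality, and the hazard ratio moves by 0.01 to 0.015 in either direction. A reader might also extend the point to time to improvement (3.3.4) and time to discharge or NEWS (3.3.5). These carry the same death rule, but SAP 8.2 does not assign them to the early set.

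Finally, the change would come after the interim results were disclosed. That calls for a note. It is a weak reason to keep the rule, since the test hardly changes and the full-set definition is left alone.

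**Conclusion.** The concern holds as a minor point. The death rule was built for complete 28-day follow-up and is carried unchanged into a data set cut at April 28. The early-set Kaplan-Meier recovery curve is therefore biased downward toward Day 29, by about 0.2 to 1.5 points at 2% mortality and 0.8 to 5.4 points at 10%, when true recovery is 70%. The direction is algebraic. The size rests on the assumed start date, accrual shape, mortality and event-time shape.

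The premise that survivors leave at the cut is inferred; it is the only workable reading of a set limited to data up to that date. That missing rule is part of the finding.

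Fine-Gray regression (8.1.2) with suitable censoring weights would handle the cut, but it is a sensitivity analysis that the SAP does not assign to the early set.

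**What to change.** In SAP 3.3.2 and 6.5 add, for the early analysis set only: *Subjects without the event who are still on study at April 28, 2020 are censored at their last assessed day on or before that date; a death before the event is censored at the earlier of 28 days and the corresponding potential follow-up time from randomization to the April 28, 2020 cut.* The word *corresponding* matters: under SAP 4.3 a recorded score describes the previous day, so deaths and survivors should be counted on the same assessed-day basis.

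Apply the rule to 3.3.4 and 3.3.5 only if those endpoints are analysed on the early set. Leave the full-set rule unchanged.

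The cost is one sentence and a one-line derivation from two known dates. The early-set curve and median may shift slightly from results already released, and the change must be recorded as made after the interim results were known.
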